9.1 Timing of analyses

The final analysis will be performed after the last patient has completed the last follow-up visit 12 months after randomisation, and all data have been transferred to a separate file. The data must have met the cleaning and approval requirements of the primary investigator, and this Statistical Analysis Plan must have been finalised and approved by the primary investigator. Only when these requirements have been met, will database lock occur, and the randomisation code be opened.

9.2 Populations for analysis

9.2.1 Full analysis set (modified intention-to-treat population)

The full analysis set (FAS) will include all patients who were randomised and who (irrespective of receipt of actual treatment) had intracoronary ultrasound adequate for the determination of coronary intima thickness at baseline and at the 12 months follow-up. The adequacy of the ultrasound examination must be determined before database lock and the randomisation code is opened. The primary analysis of the primary endpoint (and all secondary endpoints) will be carried out on the FAS.

9.2.2 Per Protocol set

The per protocol set (PPS) will include all patients who received the study drug with compliance > 80% during the treatment period (see Section 9.4) and who have valid data for the baseline and the 12-months follow-up measurements. A secondary analysis of the primary endpoint will be performed on the PPS.

9.2.3 Safety set

The safety set (SS) will include all patients who received any study treatment (including control) but excluding subjects who drop out prior to receiving treatment.

Each patient's inclusion or exclusion status regarding each analysis population must be determined prior to breaking the blind. The status must be documented in the final database prior to breaking the blind.

9.3 Covariates and Subgroups

The analyses of the primary and secondary endpoints will not be adjusted for baseline characteristics; however, the primary endpoint and key secondary endpoints will be calculated as baseline-adjusted values (i.e., the analyses of the 12 months measurements will be adjusted for the baseline measurements in ANCOVA analyses) as specified in Section 10. Adjustment will also be made for the stratification factor in the randomisation (centre).

We will perform binary subgroup analyses of the primary endpoint stratified by gender; age above/below median; baseline LDL cholesterol above/below median; baseline intima thickness above/below median; ischaemic reason for transplant; baseline CRP above/below median; and baseline creatinine above/below median. A forest plot will be used to communicate the results. The

subgroup analyses are exploratory, and the trial is not powered to show differences across subgroups.

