1.1 Cardiac allograft vasculopathy

Cardiac allograft vasculopathy is a major impediment to long-term survival in heart transplant recipients.^{12, 13} It is present in 48 % of heart transplant recipients within 10 years after transplantation,² and accounts for 30% of deaths occurring beyond the first year.³ The pathophysiology of cardiac allograft vasculopathy is not fully elucidated. The aetiology is likely to be multifactorial. Classical risk factors for coronary artery disease are thought to contribute. Donor male gender, hypertension, and diabetes are risk factors for the development of vasculopathy in the allograft,¹⁴ suggesting that pre-existing atherosclerosis predisposes to vasculopathy. Animal models have shown that hyperlipidaemia accelerates allograft vasculopathy.¹⁵⁻¹⁷ In human heart transplant recipients, there is a clear link between cholesterol levels and the risk of developing allograft coronary artery disease.¹⁸⁻²⁰ In addition to traditional risk factors for atherosclerotic disease, low grade inflammation and chronic, antibody-mediated rejection are thought to contribute to the disease process.^{12, 13}

Statin therapy reduces the prevalence of cardiac allograft vasculopathy in heart transplant recipients.⁶ Research performed at the Scandinavian transplant centres has shown that early conversion from a calcineurin-based immunosuppressive regimen to a regimen based on everolimus, an inhibitor of the mechanistic target of rapamycin, alleviates cardiac allograft vasculopathy in *de novo* heart transplant recipients.²¹ However, cardiac allograft vasculopathy remains a major obstacle in the effort to improve outcomes after heart transplantation.⁴

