5.5 Concomitant medication

All concomitant medication will be recorded in the patient's file and CRF. Study participation does not preclude administration of drugs that are provided on clinical indication. On the contrary, study participants will receive standard-of-care treatment as recommended in prevailing guidelines.

We routinely use induction therapy at the time of heart transplantation. We introduce maintenance immunosuppressive therapy consisting of a combination of a calcineurin inhibitor, mofetil mycophenolate and steroids on the first post-operative day with gradual tapering of the calcineurin inhibitor and steroid doses over the first year. In selected patients, we add everolimus with reduction of the calcineurin inhibitor dose or complete cessation of calcineurin inhibitor treatment. We perform regular bioptic controls as recommended by the International Society of Heart and Lung Transplantation (ISHLT). We administer trimethoprim-sulpha o.d. for the first 6 months after heart transplantation according to current recommendations. In patients with blood pressure consistently above 140/90, we provide anti-hypertensive treatment.

Pravastatin 40 mg o.d. is routinely introduced during the first five postoperative days and continued indefinitely unless there are contraindications to statin use, or there is a need to escalate treatment. To keep investigators blinded to treatment allocation, we will not perform measurements of blood lipids for the during the treatment phase.

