10.1 Determination of sample size

This trial is designed to assess the effect of evolocumab on intima thickness as measured by coronary IVUS. The sample size of the present study is based calculations relating to the primary outcome, the change in maximal intima thickness from baseline to one year. In the SCHEDULE trial, we observed an increase in the maximal intima thickness of 0.08 +/- 0.12 mm in the placebo group, whereas the corresponding increase was 0.03 +/- 0.06 mm in the everolimus arm.²¹ Intensive cholesterol reduction has been shown to actually reverse the atherosclerotic volume in previous trials. We therefore hope to achieve a 0.05 mm between-group difference in the change in the intima thickness in the EVOLVD trial. With an estimated 0.09 mm standard deviation, we will require 51 patients in each arm with a power of 80%, at a two sided alpha level of 5%. To increase the chances of reaching the primary and secondary outcomes, and to compensate for uncertainties in this calculation, we will ensure that 120 patients complete the one-year follow-up. To allow for a dropout rate of 5 - 10% we aim to include 130 patients.

In the SCHEDULE trial, the mean increase in the percent atheroma volume was 1.3 ± 2.3 percentage points in the everolimus arm versus 4.2 ± 5.0 percentage points in the cyclosporine group. Provided that evolocumab can produce a similar reduction in the progression of the atheroma volume, with an estimated standard deviation of 3.7 percentage points, we will need just 26 patients in each arm to detect a between-group difference in the important secondary outcome, the change in percent atheroma volume, with an α of 5 % and a power of 0.8.

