This trial is designed to assess the effect of evolocumab on intima thickness as measured by coronary IVUS. The sample size of the present study is based calculations relating to the primary outcome, the change in maximal intima thickness from baseline to one year. In the SCHEDULE trial, we observed an increase in the maximal intima thickness of 0.08 (SD 0.12) mm in the placebo group, whereas the corresponding increase was 0.03 (SD 0.06) mm in the everolimus arm.² Intensive cholesterol reduction has been shown to actually reverse the atherosclerotic volume in previous trials.³,⁴ We therefore hope to achieve a 0.05 mm between-group difference in the change in the intima thickness in the EVOLVD trial. With an estimated 0.09 mm standard deviation, we will require 51 patients in each arm with a power of 80%, at a two-sided alpha level of 5%. To increase the chances of reaching the primary and secondary outcomes, and to compensate for uncertainties in

this calculation, we will aim for 120 patients to complete the one-year follow-up. To allow for a dropout rate of 5 - 10%, we plan to include 130 patients.

9 General Considerations

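### Baseline everolimus use is recorded and is linked by the planning source to slower intimal thickening, but it is neither a covariate nor a subgroup factor; the cost is modest precision, not validity

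*SAP*

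**What the plan says.** - **Background therapy.** Protocol 5.5 allows everolimus: "In selected patients, we add everolimus with reduction of the calcineurin inhibitor dose or complete cessation of calcineurin inhibitor treatment". The share of patients is not given, nor when after transplant it is started.
- **What the documents say about everolimus.** Protocol 1.1 reports that early conversion from a calcineurin-based to an everolimus-based regimen "alleviates cardiac allograft vasculopathy in *de novo* heart transplant recipients". SAP section 8 adds figures from the earlier Scandinavian everolimus trial: "we observed an increase in the maximal intima thickness of 0.08 (SD 0.12) mm in the placebo group", while "the corresponding increase was 0.03 (SD 0.06) mm in the everolimus arm".
- **Target.** The same paragraph continues: "We therefore hope to achieve a 0.05 mm between-group difference in the change in the intima thickness".
- **Data collected.** Everolimus is in the baseline table (SAP 10.3), which is presented by arm (SAP section 10). Concomitant drugs are recorded by generic name before treatment and at later visits (Protocol 6.2.1, 6.2.3, 6.2.4).
- **Analysis.** SAP 9.3 opens with "The analyses of the primary and secondary endpoints will not be adjusted for baseline characteristics". The sentence then provides for adjustment for the baseline measurement, and the next sentence adds centre. SAP 11.2 confirms treatment, baseline value and centre as the only terms.
- **Subgroups.** SAP 9.3 lists seven factors: gender, age, LDL cholesterol, intima thickness, ischaemic cause, CRP and creatinine. None is an immunosuppressant.
- **Randomisation.** Stratified by centre only (Protocol 10.2.1, SAP 7.1.3).

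**The concern.** Everolimus is the one background treatment whose association with the primary endpoint the documents put into figures, and that figure equals the effect sought for evolocumab. The status is known before randomisation and already collected. The documents give no comparable figure for any of the seven chosen subgroup factors.

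The terms already in the model are only partial substitutes. Baseline thickness is measured 4 to 8 weeks after transplant, whereas the everolimus contrast concerns growth after that. Centre carries the information only as far as practice differs between centres, and Protocol 5.5 describes selection by patient. At stake is residual variance that one prespecified term could remove.

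**Working it through.** **Inputs.** Target difference 0.05 mm, SD 0.09 mm, two-sided 5%, 80% power, 51 per arm, 120 completers or 60 per arm (Protocol 10.1, SAP section 8). Regimen contrast 0.08 − 0.03 = 0.05 mm (same place). The share of everolimus users, p, is not stated; I assume 10 to 50%. I also assume that the full 0.05 mm applies to baseline users. The 0.09 mm is an SD of change and stands in for the ANCOVA residual SD, which the documents do not give.

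**The plan's own figure.** n = 2 × (1.960 + 0.842)² × 0.09² / 0.05² = 50.9, so 51 per arm; it reproduces. At 60 per arm the standard error is 0.09 × √(2/60) = 0.0164 mm and power is 86.1%.

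**Variance explained, if 0.09 mm already includes the everolimus mix.** R² = p(1 − p) × 0.05² / 0.09². Adjusted SD = 0.09 × √(1 − R²).

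| p | R² | Adjusted SD (mm) | n per arm | Power at 60 per arm | Gain (points) |
|---|---|---|---|---|---|
| 10% | 2.8% | 0.0887 | 50 | 87.0% | 0.9 |
| 20% | 4.9% | 0.0877 | 49 | 87.7% | 1.7 |
| 30% | 6.5% | 0.0870 | 48 | 88.2% | 2.2 |
| 50% | 7.7% | 0.0865 | 47 | 88.6% | 2.6 |

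Because p(1 − p) peaks at 50%, 7.7% is the ceiling for any share under these inputs.

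**If 0.09 mm is instead the SD within a regimen.** Leaving everolimus out raises the SD to √(0.09² + p(1 − p) × 0.05²) = 0.0912, 0.0922, 0.0929 or 0.0934 mm at 10, 20, 30 or 50% use. Required n becomes 53, 54, 55 or 55 per arm. Power at 60 per arm falls from 86.1% to 85.1, 84.4, 83.9 or 83.5%. The size is the same, seen from the other side.

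**Chance imbalance.** The SD of the shift in the estimate is 0.05 × √(2p(1 − p)/60) = 0.0027 mm (10%) to 0.0046 mm (50%). At 50% use, (0.0046/0.0164)² is about 7.7%, which is the R² in the table. Chance imbalance is therefore the same quantity as the extra variance, already inside the 0.0164 mm standard error, and must not be counted again.

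**Validity.** This was simulated with 60 per arm and 8,000 trials per setting, with SD 0.06 mm in users and 0.12 mm in others, as in the planning source; centre and baseline value were not modelled. Type I error without the everolimus term was 5.0 to 5.1%, and mean estimates lay within 0.0005 mm of the truth. Power without and with the term was 63.6% and 63.8% (10% use), 71.1% and 72.5% (30%), and 79.0% and 81.4% (50%). Levels are lower because the SD of 0.12 mm in non-users exceeds the planning value; the gains, 0.2 to 2.4 points, are again small.

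**What a subgroup row can show.** At 20% use there are about 12 users per arm. The standard error of the effect in users is 0.09 × √(2/12) = 0.037 mm, a 95% interval of about ±0.07 mm, wider than the target itself.

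**The case against.** The strongest reply is that this is an optional refinement.

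- **Randomisation protects the comparison.** Omitting a prognostic covariate causes neither bias nor type I inflation, and the simulation agrees. The plan also holds 60 completers per arm against 51 required, partly to cover uncertainty in the calculation. This stands.
- **The 0.05 mm is not the effect of a baseline yes/no flag.** It is a randomised contrast between regimens: early conversion with withdrawal of the calcineurin inhibitor. In EVOLVD, use is selective, may involve only a reduced calcineurin-inhibitor dose, and reflects the reasons for selection; tacrolimus is in use as well as cyclosporine. This stands, so the figures above are conditional.
- **Prevalence is unknown.** Selected patients does not suggest 50%, where the gain is largest. Baseline falls 4 to 8 weeks after transplant, so later starters are missed. This stands.
- **Centre and baseline thickness are in the model** and may absorb part of the gain. This stands, though selection within centre would remain.

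A reader might infer more: that a null result could not be interpreted because everolimus users have little progression left to prevent, and that adjustment would cure this. The arithmetic behind that reading is 0.08 − 0.05p for placebo progression, 0.075 to 0.055 mm at 10 to 50% use, which makes the target 67 to 91% of it. The documents do not support the inference. They rest the target partly on reversal of atheroma, so placebo progression is not a ceiling, and they say nothing about evolocumab's effect in everolimus users. A covariate cannot explain a null result, and a subgroup interval of about ±0.07 mm could hardly do so.

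These points limit the expected gain. They give no reason to leave out an informative variable that is already collected.

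**Conclusion.** The omission is real and worth correcting, as a matter of precision only. The primary test remains valid and unbiased. If the 0.05 mm regimen contrast carried over and 10 to 50% of patients used everolimus at baseline, adjustment would remove about 3 to 8% of the variance and add roughly 1 to 2.5 power points at 60 per arm, less whatever centre and baseline thickness already take up. If the effect of selective use is smaller, or users are few, the gain approaches zero.

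Three stronger readings should not be drawn: that the planned comparison is confounded, that chance imbalance is a further harm, or that the documents show everolimus as used here to slow the endpoint by the full 0.05 mm.

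Separately, and only as a clerical matter, Protocol 10.1 labels the comparator of the earlier trial as placebo in one paragraph and as cyclosporine in the next, and SAP section 8 repeats placebo. The label should be reconciled, but it has no bearing on the covariate.

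**What to change.** Before database lock and opening of the randomisation code:

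1. In SAP 9.3 and 11.2, add everolimus at baseline (yes/no, defined as use at randomisation) as a prespecified covariate, beside baseline value and centre, in the ANCOVAs for maximal intimal thickness and percent atheroma volume. If the sponsor prefers to keep the primary model, prespecify the same model as a supportive ANCOVA.
2. Add baseline everolimus as one exploratory subgroup row in the forest plot, with no claim that it will account for a null result.
3. Tabulate by arm the patients who start everolimus after randomisation. Do not adjust for this, because it occurs after allocation.

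The cost is SAP wording, one degree of freedom, one forest-plot row and one table from data already collected. The downside is negligible gain if few patients use everolimus at baseline. Protocol 10.4 permits changes to the plan until database lock; after unblinding, the same analysis would be post hoc.

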9.4 Missing Data

Because the measurements of the primary endpoint and key secondary endpoints are collected twice only, and the endpoint analyses will be baseline adjusted ANCOVA, there will be no imputation of missing data in the primary analyses, which will be analysed on the FAS. However, to elucidate possible biases this method entails, baseline data (see Section 9.3) for patients for whom endpoint data exist will be tabulated along with baseline data for patients who for some reason drop out or are unable to complete both sets of tests. Any noteworthy differences will be commented on. We will also describe the dropout rate in each treatment arm and comment on any important differences. The extent of missing data will be reported for each endpoint variable.

The impact of missing data for the primary endpoint will be assessed with sensitivity analyses (see Section 10.4).

We expect few missing values on baseline characteristics and will not employ a strategy to impute missing baseline values.

10 Summary of Study Data

[figure not shown]
We will present the baseline characteristics by columns for each treatment (placebo, evolocumab) on the FAS. All continuous variables will be summarised using the following descriptive statistics: mean ± standard deviation; median (interquartile range). The frequency and percentages (based on the non-missing sample size) of observed levels will be reported for all categorical measures.

10.1 Subject Disposition

We will document how many subjects reached the various stages of the trial (the number screened, randomised, had 12-month follow-up, and could be analysed for the primary endpoint), and how many dropped out and for what reasons (death, withdrew consent, failed to show up) according to the following CONSORT diagram:

10.2 Consort diagram

10.3 Baseline Characteristics

The following baseline variables will be presented.

De				-	ᆫ	
176	т	()!	па	п	п	v

Age, years

Male sex

Smoker, current/previous smoker

Body mass index, kg/m²

Systolic blood pressure, mmHg

Diastolic blood pressure, mmHg

Heart rate, rpm

Time from transplant

Donor age

Cold ischaemia time

Medical history

Cause of heart failure

- Ischaemic
- Dilated cardiomyopathy
- Congenital heart disease
- Othe

Hypertension

Hypercholesterolemia

Previous stroke or transient ischemic attack

Chronic obstructive pulmonary disease

Medication (No of patients)

Tacrolimus

Cyclosporine

Everolimus

MMF

Prednisone

Statin

Ezetimibe

Anticoagulant

Platelet inhibitor

Beta blocker

Angiotensin converting enzyme inhibitor or angiotensin receptor

blocker

Calcium channel blocker

Diuretic

Biochemistry

Haemoglobin, g/dL

N-terminal pro-B-type natriuretic peptide

(NT-proBNP), ng/L

P-troponin T, ng/L

C-reactive protein (CRP), mg/L

Creatinine, µmol/L

Estimated glomerular filtration rate (eGFR), mL/min

Total cholesterol mmol/L

LDL cholesterol, mmol/L	
HDL cholesterol, mmol/L	
Triglycerides, mmol/L	
ALT (Units/L)	

10.4 Treatment Compliance

Study drug injections are made on-site at 0, 1, 2, 3, 6, and 9 months, whereas patients self-inject on months 4, 5, 7, 8, 10, and 11. The patients deliver empty boxes for the estimation of drug compliance after self-administration. Treatment compliance (in percent) for each patient is calculated as 100 times the number of study drug injections (observed and estimated based on the delivery of empty boxes) divided by 12 (max number of injections). We will consider a patient with compliance > 80% as a treatment complier to be included in the PPS. Patients who die during follow-up, withdraw from the trial, or who demonstrate contraindications to the study drug will be considered non-compliers. We will report the average and SD of treatment compliance and the number and percentage of treatment compliers and non-compliers by each treatment arm.

11 Statistical analyses of primary and secondary endpoints

11.2 Continuous endpoints measured at two points in time

Continuous variables measured at baseline and 12 months' follow-up only, including the primary endpoint, percent atheroma volume, and cardiac allograft vasculopathy, will be performed as analysis of covariance (ANCOVA) in the full analysis set. The model will be a linear regression with

the 12 months' follow-up measurement as the outcome (dependent) variable and treatment allocation (0=placebo, 1 = Evolocumab), baseline value, and centre (stratification factor in the randomisation) as explanatory (independent) variables. The effect measure will be the beta-coefficient for treatment allocation (the between-group difference), estimated with a 95% confidence interval. For the primary endpoint only, we will also report the two-sided p-value for the null hypothesis of a zero-treatment effect.

The observed data and the estimated between-group difference from the ANCOVA analyses will be illustrated with the regression lines for placebo and Evolocumab superimposed on a scatter plot of the baseline measurements (x-axis) and the 12-months follow-up measurements (y-axis).

11.3 Continuous endpoints measured at more than two points in time

A linear mixed model will be fitted to all continuous endpoints with more than two measurements (LDL, NT-proBNP, TnT). Treatment, visit, treatment x visit interaction, and centre (stratification factor in the randomisation) will be fixed factors. A random intercept will be used. Based on the fitted model, we will estimate treatment group means with 95% confidence intervals for baseline, end of treatment time points, and changes from baseline to end of treatment. We will also estimate (with a 95% CI) the between-group difference in changes from baseline to end of treatment.

The observed values of LDL for each measured time point will be plotted as a connected line plot with error bars (showing the SD) for each treatment arm.

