10.5 Statistical analysis

All statistical tests will be performed using a two-sided 5 % level of significance. Continuous efficacy variables will be analysed using baseline-adjusted ANCOVA for comparisons between the treatment arms. If necessary, values will be log-transformed to meet the assumptions of the tests. All analyses will primarily be analysed according to the intention-to-treat principle. The number of major clinical events will be analysed using descriptive statistics. Between-group differences in ordinal categorical variables, such as NYHA class, will be analysed using ordinal logistic regression, whereas the count variables will be assessed by Poisson regression. Demographic, efficacy and safety data will be summarised by treatment group using means, minimums, medians, maximums, interquartile ranges and standard deviations for continuous variables and frequency counts and percentages for categorical variables. Per protocol analyses will be performed using the same methods as for the intention-to-treat analyses.

The primary endpoint, the between-group difference in the baseline-adjusted intima thickness at 12 months, will be calculated by baseline-adjusted ANCOVA according to the intention-to-treat principle, the statistical null-hypothesis being that the intima thickness does not differ between the two treatment arms. Secondary analyses will be made according to the per-protocol-principle as baseline-adjusted absolute values after end-of-treatment.

Key, secondary endpoints:

The secondary endpoints "Percent atheroma volume as measured by IVUS" and "Cardiac allograft vasculopathy" will be tested, at a two-sided alpha level of 0.05, in a hierarchical fashion. The baseline-adjusted between-group difference in the atheroma volume, eGFR, quality of life, and biomarkers reflecting cardiac function, blood lipids, and inflammation will be calculated by ANCOVA according to the intention to treat principle. The statistical null-hypotheses are that the changes in these characteristics do not differ between patients allocated to evolocumab and patients allocated to placebo.

Secondary per protocol analyses will be performed using the same methods as for the intentionto-treat analyses. Exploratory analyses will be made for efficacy variables stratified by centre.

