7.1 General Study Design and Plan

This is a phase II, multi-centre, randomised, placebo controlled, double blind, parallel group trial. The trial is conducted at the six Nordic transplant centres in Aarhus, Copenhagen, Helsinki, Gothenburg, Lund, and Oslo. Eligible patients are randomised 1:1 and allocated to subcutaneous evolocumab or matching placebo at baseline, after providing written informed consent and performing baseline exams. The patients start treatment with 420 mg evolocumab/placebo immediately after randomisation. The study is designed to show superiority regarding the primary endpoint in patients assigned to active treatment versus patients allocated to the placebo arm.

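### SAP 11.3 fixes no analysis scale for NT-proBNP and troponin T, and its random-intercept model could give imprecise or undercovering intervals if these markers are skewed or fall after baseline

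*SAP*

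**What the plan says.** NT-proBNP and troponin T are two of the five secondary endpoints in SAP 6.2.2. The SAP's endpoint table ties them to the cardiac-function objective and has them measured at baseline and at 1, 2, 3, 6, 9 and 12 months.

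SAP 11.3 gives the model: "A linear mixed model will be fitted to all continuous endpoints with more than two measurements (LDL, NT-proBNP, TnT". Treatment, visit, their interaction and centre are fixed effects, with a random intercept per patient. From this fit, "we will estimate treatment group means with 95% confidence intervals for baseline, end of treatment time points", along with changes from baseline and the between-group difference in those changes. The section names no transformation, residual check or ratio-type effect.

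Protocol 10.5, writing about an ANCOVA plan for continuous efficacy variables, adds: "If necessary, values will be log-transformed to meet the assumptions of the tests". It gives no criterion for when this applies. The SAP neither repeats the clause nor withdraws it.

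Under SAP 11.1 no secondary endpoint is tested. Each gets an unadjusted 95% confidence interval, and the results are to be read as supportive or exploratory.

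**The concern.** Both markers are positive concentrations, for which right skew and a spread that rises with level are reasonable working assumptions. Baseline is 4–8 weeks after transplantation, so a fall over the following year is plausible, though the documents do not say so.

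The scale is unsettled on either reading. If SAP 11.3 means what it literally says, the original scale is used and no transformation is available. If the protocol clause still applies, somebody chooses the scale after seeing the data, with no stated rule.

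Two things are at stake. On a skewed raw scale the intervals may be much less precise than they need be. And a random-intercept model has a single residual variance; if the variance shrinks as levels fall, the pooled value understates the baseline variance and the standard error of the change contrast is too small. Since the interval is the only inference reported for these endpoints, its width and coverage are the result.

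**Working it through.** **1. The plan's own figure.** SAP section 8 assumes a "0.05 mm between-group difference in the change in the intima thickness" and continues: "With an estimated 0.09 mm standard deviation". Then n per arm = 2 × (1.96 + 0.84)² × (0.09/0.05)² = 2 × 7.85 × 3.24 = 50.9, so 51, as stated. There is no comparable figure for NT-proBNP or troponin T to reproduce.

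**2. Inputs.** From the documents: 60 per arm ("we will aim for 120 patients to complete the one-year follow-up", allocated 1:1), seven visits, random intercept only. Assumed: log-normal values; log-SD 0.4 to 1.2; a 12-month level equal to baseline, halved, or lower; complete data; log-scale correlation 0.6 between visits unless serial correlation is stated.

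**3. Precision, flat levels.** The large-sample efficiency of raw against logged means is s²/(exp(s²) − 1), with s the log-SD. At s = 0.8 this is 0.64/(1.896 − 1) = 0.71. The last two columns are simulated shares of 95% intervals that exclude no effect at a true ratio of 0.7, used here only as a yardstick for precision.

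| log-SD | efficiency | raw | log |
|---|---|---|---|
| 0.4 | 0.16/0.174 = 0.92 | 99.9% | 100% |
| 0.8 | 0.64/0.896 = 0.71 | 52% | 78% |
| 1.1 | 1.21/2.353 = 0.51 | 24% | 49% |
| 1.2 | 1.44/3.221 = 0.45 | 20% | 44% |

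**4. Coverage on the raw scale.** With complete data the estimate is the difference in mean change, and the model's SE is √(4 × s2/60), where s2 is the pooled within-patient residual mean square. As a hand check, let the level drop to a fraction f straight after baseline, with raw variance v at baseline and f²v at the six later visits, and ignore correlation between visits. A patient's change has true variance v(1 + f²); the model uses 2v(1 + 6f²)/7.

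- f = 1: both are 2v, so coverage is 95%.
- f = 0.5: true 1.25v, model 0.714v. SE ratio √(0.714/1.25) = 0.756; 1.96 × 0.756 = 1.48; coverage about 86%.
- f = 0.25: true 1.0625v, model 0.393v. SE ratio 0.608; 1.96 × 0.608 = 1.19; coverage about 77%.

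Simulations with a gradual fall, and no treatment effect or a modest one, agree: 94–95% with flat levels, 86–90% if the level halves, 77–83% with a four-fold fall, and 71–73% with a ten-fold fall.

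**5. Which feature causes it.**

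- Same raw contrast, SE taken from the observed changes so that no common variance is imposed: 94.8–96.4%.
- Log scale, random intercept, visits equally correlated: 93.6–95.7%.
- Log scale, random intercept, serial correlation: 90–92% under one assumed pattern, 85–86% under another (correlation 0.9 per month).
- Either scale under that last pattern, random-intercept restriction lifted: about 94–96%.

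The precision loss in step 3 therefore belongs to the scale. The undercoverage belongs to the common-variance, random-intercept structure as well, and logging removes only the part due to variance changing with level.

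**The case against.** A reader might infer that the SAP has deliberately abandoned log transformation, that the intervals will therefore be wrong, and that logging would put them right. The documents and the check do not support that reading.

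- SAP 11.3 is silent on scale. It does not say untransformed and does not revoke Protocol 10.5. Means and differences in change suggest the original scale, but that is an inference.
- Skewness alone does little harm to coverage at 60 per arm: with flat levels it stays near 95%. Undercoverage needs a marked fall in level, which the documents do not describe.
- Raw-scale coverage can be repaired without logging, and logging with only a random intercept can still undercover.
- The precision loss depends on a log-SD that the documents do not give, and with flat levels it is negligible at 0.4.
- SAP 11.1 rules out definitive conclusions from these endpoints. SAP section 10 already plans medians and interquartile ranges for the baseline variables, which include both markers.

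All of this stands, and it limits the claim to a conditional one. It does not settle the scale: silence plus a conditional clause still leaves that choice open at analysis. In none of the simulated settings was the log scale materially worse.

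**Conclusion.** The point holds in conditional form. SAP 11.3 leaves the scale for two secondary endpoints either implicitly raw or open to a data-driven choice, and its covariance structure is too restrictive to guarantee coverage on either scale.

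If the log-SD is about 0.8 to 1.1, the raw scale costs roughly 25 percentage points in the share of intervals excluding no effect at a true ratio of 0.7 (78 − 52 = 26; 49 − 24 = 25). If levels also fall, nominal 95% raw-scale intervals for the difference in change cover about 90% (halving) or about 80% (four-fold fall). These sizes rest on assumed log-normality, spread, correlation and time course. The analysis of the primary endpoint is not touched.

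**What to change.** Before database lock and unblinding, amend SAP 11.3 for NT-proBNP and troponin T:

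- Analyse both on the natural-log scale as a fixed choice. Report the evolocumab/placebo ratio of geometric means with its 95% confidence interval, and show raw medians and interquartile ranges descriptively.
- Replace the random-intercept-only structure with an unstructured covariance across the seven visits, or use robust standard errors.

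Protocol 10.4 permits changes to the analysis plan until database lock, and SAP 9.1 requires the SAP to be final before the code is opened. The cost is a few lines of text. The effect is then read as a ratio and not as a difference in ng/L.
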